Pharmacokinetic and Pharmacogenomic Endpoints:

Plasma brexpiprazole concentrations, CYP2D6 genetic testing

Statistical Methods:

Statistical Methods for Primary Endpoints:

The primary endpoint is mean changes from baseline (Week 8 of the antidepressant treatment period [Phase A]) in MADRS total scores at Week 6 of the double-blind period (Phase B). For the primary analysis, Mixed-model Repeated Measure (MMRM) analysis will be performed using the observed cases data set in full analysis set. The statistical hypotheses will be tested, based on differences in least square means between each brexpiprazole group and the placebo group, which are calculated by MMRM. To adjust for multiplicity of tests, due to there being 2 comparisons with the placebo group, a fixed-sequence approach will be used to control overall type 1 error rates. Comparison between the brexpiprazole 2 mg/day group and placebo group will be performed first; only when significance is observed at a two-sided significance level of 5%, will comparison between the brexpiprazole 1 mg/day group and placebo group be

performed at a two-sided significance level of 5%.

The MMRM will include treatment group (brexpiprazole 1 mg/day group, brexpiprazole 2 mg/day group, and placebo group), time point (double-blind period [Phase B] Weeks 1, 2, 3, 4, 5, and 6), and interaction between treatment group and time point as factors, and baseline and interaction between baseline and time point as covariates. Unstructured error variance-covariance structure will be assumed. For a degree-of-freedom approximation, the Kenward-Roger method will be used.

For each time point, least square means of each treatment group and differences in least square means between each brexpiprazole group and the placebo group, as well as the two-sided 95% confidence intervals (CIs) will be determined.

Rationale for target number of subjects:

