In phase 3, double-blind, placebo-controlled trials of fixed doses of brexpiprazole (331-10-227, 331-10-228, and 331-13-214) conducted outside Japan, changes from baseline in MADRS total scores at Week 6 of the double-blind period (Phase B) have been analyzed by the MMRM method (for 331-10-227 and 331-10-228 trials, based on the results for efficacy from an analysis of subgroups meeting the inclusion criteria that had been revised in the middle of the trials). which demonstrated that the differences between the brexpiprazole groups (the 3 mg group in 331-10-227 trial, and the 2 mg group in 331-10-228 and 331-13-214 trials) and the placebo group were -1.9, -3.2, and -2.3, respectively, and that the standard deviations obtained from standard errors and numbers of subjects at Week 6 of the double-blind period (Phase B) were 7.2, 7.7, and 8.2, respectively. On the assumption that the difference in changes from baseline in MADRS total scores at Week 6 of the double-blind period (Phase B) is -2.4 for the brexpiprazole group compared with the placebo group with a standard deviation of 7.7, this trial will require 218 subjects per group to ensure a power of 90% in a twosided test with a significance level of 0.05. We have decided that the planned number of subjects for randomization will be 240 per group, assuming that 7% of subjects will discontinue the trial during the double-blind period (Phase B) and some subjects will be excluded from analysis.

Trial Duration: 01 Jun 2018 to 31 Jul 2022 (planned)

Table of Contents

| Protocol Synopsis | | 2 |
|-------------------|--|----|
| Table | of Contents | 13 |
| List of | In-text Tables | 19 |
| | In-text Figures | |
| | Appendices | |
| | Abbreviations and Definitions of Terms | |
| 1 | Introduction | |
| 1.1 | Nonclinical Data | |
| 1.2 | Clinical Data | |
| 1.2.1 | Clinical Data From Japanese Trials in Subjects With Schizophrenia | |
| 1.2.1.1 | Dose-finding Trial in Subjects With Schizophrenia (331-10-002) | 28 |
| 1.2.1.2 | Long-term Trial in Subjects With Schizophrenia (331-10-003) | 29 |
| 1.2.2 | Clinical Data From Overseas Trials in Subjects With Major Depressive Disorder | 29 |
| 1.2.2.1 | Confirmatory Trial in Subjects With Major Depressive Disorder (331-10-227) | 29 |
| 1.2.2.2 | Confirmatory Trial in Subjects With Major Depressive Disorder (331-10-228) | 30 |
| 1.2.2.3 | Confirmatory Trial in Subjects With Major Depressive Disorder (331-13-214) | 31 |

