7.1 Determination of Sample Size

In phase 3, double-blind, placebo-controlled, fixed dose trials of brexpiprazole (331-10-227, 331-10-228, and 331-13-214) conducted outside Japan, changes from baseline in MADRS total scores at Week 6 of the double-blind period (Phase B) have been analyzed by the Mixed-model Repeated Measure (MMRM) method (for 331-10-227 and 331-10-228, based on the results for efficacy from an analysis of subgroups meeting the inclusion criteria that had been revised in the middle of the trials), which demonstrated that the differences between the brexpiprazole groups (the 3 mg group in 331-10-227, and the 2 mg group in 331-10-228 and 331-13-214) and the placebo group were -1.9, -3.2, and -2.3, respectively, and that the standard deviations obtained from standard errors and numbers of subjects at Week 6 of the double-blind period (Phase B) were 7.2, 7.7 and 8.2, respectively. On the assumption that the difference in changes from baseline in MADRS total scores at Week 6 of the double-blind period (Phase B) is -2.4 for the brexpiprazole group compared with the placebo group with a standard deviation of 7.7, this trial will require 218 subjects per group to ensure a power of 90% in a two-sided test with a significance level of 0.05. We have decided that the planned number of subjects for randomization will be 240 per group, assuming that 7% of subjects will discontinue the trial during the double-blind period (Phase B) and some subjects will be excluded from analysis.

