5.2 Full Analysis Set

The full analysis set (FAS) will comprise subjects who, after randomization, have received at least 1 dose of the IMP in the double-blind period (Phase B), and from whom MADRS total scores have been obtained at baseline and at least 1 time point after initiation of the treatment.

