7.6 Protocol Deviations

In randomized subjects, numbers and proportions of subjects with major deviations from the protocol will be determined for each deviation category (treatment-related deviations, eligibility-related deviations, a failure to discontinue the trial when the subject meets the withdrawal criteria, procedure-related deviations that affect evaluation of the primary endpoint, use of prohibited medications, and overall) and each trial site, overall, for each treatment group, and for the overall brexpiprazole group.

In non-randomized subjects, similar summarization will be performed overall and for each requisite concomitant medication.

8 Efficacy Analysis

Efficacy analysis in the double-blind period (Phase B) will be performed using the FAS. Unless otherwise stated, the efficacy analysis described in this section relates only to the double-blind period (phase B).

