8.1.2 Sensitivity Analyses

8.1.2.1 Sensitivity Analysis for Handling of Missing Data

As a sensitivity analysis for handling of missing data, placebo multiple imputation and tipping point analysis on MNAR assumption will be performed using a pattern-mixture model with multiple imputation.

Multiple imputation analysis will be performed according to the following procedure. The number of imputations will be 100.

- 1) The Markov Chain Monte Carlo (MCMC) method will be used to impute intermittent missing data to produce a monotone missing data pattern.
- 2) The monotone regression method will be used to impute monotone missing data.
- 3) The same MMRM as that of the primary efficacy analysis will be used to analyze the multiple-imputed datasets.
- 4) The MIANALYZE procedure will be used to integrate the analysis results of the multiple-imputed datasets, and the estimate of the difference between each brexpiprazole group and the placebo group at Week 6 in the double-blind period (Phase B) and its 95% CI and p-value will be determined.

In placebo multiple imputation, for discontinued subjects in each brexpiprazole group, MNAR will be assumed for missing data after discontinuation and an imputation model based on the placebo group will be used in imputation.

In tipping point analysis, for subjects in each brexpiprazole group who discontinued treatment for any of the following reasons, MNAR will be assumed for missing data after discontinuation.

- Withdrawal for any reason
- Withdrawal due to AEs, a lack of efficacy, or consent withdrawal
- Withdrawal due to AEs or a lack of efficacy

For subjects in each brexpiprazole group who discontinued treatment for reasons assumed as MNAR, the MAR assumption will be used to impute post-discontinuation missing data, add Δ (intergroup differences in MMRM of the primary efficacy analysis) \times k% to the imputed value, and increase k until a statistically significant conclusion is reversed ($p > 0.05$).

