CT-5.8.3 Summary of Mean Change From Baseline to Phase A and Phase A+ by Study Week in SDS Scores (Phase A Plus Sample)

CT-5.9.1 Summary of Mean Change From Baseline (End of Phase A) to Phase B by Study Week in MADRS-S Total Score - MMRM (Full Analysis Set)

CT-5.9.2 Summary of Mean Change From Baseline to Phase A by Study Week in MADRS-S Total Score (ADT Sample)

CT-5.9.3 Summary of Mean Change From Baseline to Phase A and Phase A+ by Study Week in MADRS-S Total Score (Phase A Plus Sample)

CT-5.10.1 Summary of Mean CGI-I Score by Study Week in Phase B Relative to Baseline (End of Phase A) - LOCF (Full Analysis Set)

CT-5.10.2 Summary of Mean CGI-I Score by Study Week in Phase B Relative to Baseline (End of Phase A) - OC (Full Analysis Set)

CT-5.11.1 Sensitivity Analysis of MNAR Using Tipping Point Analysis in MADRS Total Score Assume All Dropouts as MNAR (Full Analysis Set)

CT-5.11.2 Sensitivity Analysis of MNAR Using Tipping Point Analysis in MADRS Total Score Dropout due to AE or LOE or Withdraw Consent as MNAR (Full Analysis Set)

CT-5.11.3 Sensitivity Analysis of MNAR Using Tipping Point Analysis in MADRS Total Score Dropout due to AE or LOE as MNAR (Full Analysis Set)

CT-5.11.4 Sensitivity Analysis of MNAR Using Placebo Based Imputation in MADRS Total Score (Full Analysis Set)

CT-5.11.5 Summary of Mean Change From Baseline (End of Phase A) to Phase B by Study Week in MADRS Total Score - MI Wilcoxon Rank Sum Test, MI Robust Regression (Full Analysis Set)

CT-5.11.6 Summary of Mean Change From Baseline (End of Phase A) to Phase B by Study Week in MADRS Total Score - OC Wilcoxon Rank Sum Test, OC Robust Regression (Full Analysis Set)

CT-6.1.1 Summary of Mean Change From Baseline (End of Phase A) to Phase B by Study Week in MADRS Total Score by ADT: Duloxetine - MMRM (Full Analysis Set)

CT-6.1.2 Summary of Mean Change From Baseline (End of Phase A) to Phase B by Study Week in MADRS Total Score by ADT: Escitalopram - MMRM (Full Analysis Set)

CT-6.1.3 Summary of Mean Change From Baseline (End of Phase A) to Phase B by Study Week in MADRS Total Score by ADT: Fluvoxamine - MMRM (Full Analysis Set)

CT-6.1.4 Summary of Mean Change From Baseline (End of Phase A) to Phase B by Study Week in MADRS Total Score by ADT: Milnacipran - MMRM (Full Analysis Set)

CT-6.1.5 Summary of Mean Change From Baseline (End of Phase A) to Phase B by Study Week in MADRS Total Score by ADT: Paroxetine - MMRM (Full Analysis Set)

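### The MNAR sensitivity analyses run on the FAS, so the all-dropouts tipping point omits treated dropouts with no usable post-baseline MADRS; this can only overstate robustness, by an amount the documents do not fix

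*Protocol*

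**What the plan says.** SAP Section 5.2 (and Protocol Section 7.2.2) admits to the FAS a randomised subject who took at least one Phase B dose and "from whom MADRS total scores have been obtained at baseline and at least 1 time point after initiation of the treatment". The safety analysis set asks only for the dose.

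For the primary analysis, the Protocol Synopsis says that "Mixed-model Repeated Measure (MMRM) analysis will be performed using the observed cases data set in full analysis set". SAP Section 8 carries the same population to everything else: "Efficacy analysis in the double-blind period (Phase B) will be performed using the FAS".

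SAP Section 8.1.2.1 then relaxes the MAR assumption. In the placebo-based imputation, "for discontinued subjects in each brexpiprazole group, MNAR will be assumed for missing data after discontinuation". The tipping-point analysis uses three sets of discontinued brexpiprazole subjects, the widest being withdrawal for any reason. It shifts their imputed values by k% of the estimated treatment difference and raises k until significance is lost. In SAP Appendix 5, CT-5.11.1 is titled "Sensitivity Analysis of MNAR Using Tipping Point Analysis in MADRS Total Score Assume All Dropouts as MNAR (Full Analysis Set"; CT-5.11.2 to CT-5.11.4 carry the same population label. No version on all treated subjects is listed.

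Two provisions decide who reaches the FAS. MADRS is also scheduled at discontinuation in Phase B (Protocol Section 3.7.2.1 and Table 3.7-2). SAP Section 3.4 assigns Days 2 to 10 to Week 1 and discards data obtained 7 days or more after the last double-blind dose.

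On expected losses, the sample-size rationale (Protocol Synopsis and Section 7.1) sets its randomisation target "assuming that 7% of subjects will discontinue the trial during the double-blind period (Phase B) and some subjects will be excluded from analysis". It gives no count of treated subjects without a score.

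**The concern.** For the primary MMRM, dropping a subject with no post-baseline score costs nothing, because under MAR that subject adds no information on change from baseline. The MNAR analyses are different. They ask how badly unobserved subjects would have to do before the conclusion fails, and a subject with no outcome at all is the clearest case of an unobserved subject. On the FAS that subject is neither imputed nor shifted, so a table whose title speaks of all dropouts covers only the dropouts in the FAS.

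The direction is fixed. At a given MAR estimate and standard error, fewer shifted brexpiprazole subjects means a larger k before p exceeds 0.05. Likewise, fewer subjects imputed from the placebo model leaves the placebo-based estimate closer to the MAR estimate. At stake is how robust the trial is reported to be, not the primary result.

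**Working it through.** **Inputs.** Protocol Section 7.1 assumes that the difference "is -2.4 for the brexpiprazole group compared with the placebo group with a standard deviation of 7.7", and that "this trial will require 218 subjects per group to ensure a power of 90% in a two-sided test with a significance level of 0.05". It randomises 240 per group and expects 7% to discontinue. Neither document gives the number of treated subjects with no usable post-baseline MADRS, so that number, x per group, is varied from 0 to 5.2.

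**The plan's own figure.** The normal approximation gives n = 2 × (1.96 + 1.2816)² × (7.7/2.4)² = 216.3, so 217. The t-based calculation gives power 0.8996 at 217 and 0.9009 at 218, so 218 reproduces. Then 218/0.93 = 234.4, so 235. At 240, expected dropouts are 240 × 0.07 = 16.8, completers 223.2, and the margin over 218 is 5.2.

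**Approximation.** Let f be the share of the brexpiprazole group that is imputed and shifted, with the shift in the worsening direction. The estimate becomes -2.4 × (1 - f × k). Significance is lost at

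k = (2.4 - 1.96 × SE) / (f × 2.4), with SE = 7.7 × √(2/n observed).

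For a given x, both populations have the same observed subjects, so SE cancels and k(FAS)/k(all treated) = f(all treated)/f(FAS).

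- With x = 0: SE = 7.7 × √(2/223.2) = 0.729, f = 16.8/240 = 0.07, k = (2.4 - 1.429)/0.168 = 578%.
- Case A, the x subjects are among the 16.8 dropouts: f(all) = 16.8/240, f(FAS) = (16.8 - x)/(240 - x).
- Case B, they are additional: f(all) = (16.8 + x)/240, f(FAS) = 16.8/(240 - x), n observed = 223.2 - x.

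| x per group | A: k all treated | A: k FAS | A: ratio | B: k all treated | B: k FAS | B: ratio |
|---|---|---|---|---|---|---|
| 0 | 578% | 578% | 1.00 | 578% | 578% | 1.00 |
| 1 | 578% | 612% | 1.06 | 544% | 574% | 1.06 |
| 2 | 578% | 651% | 1.13 | 513% | 570% | 1.11 |
| 3 | 578% | 695% | 1.20 | 486% | 565% | 1.16 |
| 4 | 578% | 746% | 1.29 | 461% | 561% | 1.22 |
| 5.2 | 578% | 819% | 1.42 | 434% | 556% | 1.28 |

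The ratio reaches 1.25 at x of about 3.6 in Case A and 4.6 in Case B.

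**Cross-check.** Take SE from the size of the analysis set instead, with 17 other dropouts and the x subjects additional. The tipping points in MADRS points, FAS against all treated, are 14.3 and 13.6 for x = 1 (5%), 14.2 and 12.9 for x = 2 (10%), and 13.9 and 11.2 for x = 5 (25%).

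**Placebo-based estimate.** Approximated as -2.4 × (1 - f). In Case A it is -2.232 on all treated, against -2.251 on the FAS for x = 2 and -2.281 for x = 5.2. The largest gap is 0.049/2.232 = 2.2%.

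This is a large-sample approximation. It takes the same MAR estimate in both populations and ignores the extra multiple-imputation variance, which should largely cancel in the ratio.

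**The case against.** The strongest reply is that few subjects can fall into the gap. MADRS is scheduled at discontinuation, and a visit from Day 2 counts as Week 1, so most early leavers who attend it will be in the FAS. Protocol Sections 3.8.3.3 and 3.8.3.4 also press for continued follow-up. This stands, and it pushes the likely number down. It does not bring it to zero: the first scheduled Phase B score is at Day 8 ± 1, Table 3.7.1.9-1 sets no deadline for the discontinuation examination, and scores from 7 days after the last dose are discarded. Subjects lost to follow-up may supply nothing.

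The second reply is that the effect is immaterial at the design values. k stays above 430% in every scenario, and the placebo-based estimate barely moves. This also stands, and it is why the severity is low. In Case A, however, the ratio does not depend on the observed effect, so the same proportional overstatement would apply if the trial result were closer to the margin.

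Three stronger readings are tempting.

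- A reader might take the margin of about 5 per group (223 - 218) as the expected number with no score and quote 25% as the size of the error. The sample-size text gives neither a number nor a reason for exclusions. They could include subjects never dosed or without a baseline score, whom the fix would not add, and 240 may simply be 235 rounded up. Adding 5 to 17 also gives 22/240 = 9.2% discontinuing, against the stated 7%.
- A reader might infer imbalance between groups from the adverse-event discontinuation rates in the overseas 2 mg trials (3.2% against 0.0%, and 2.1% against 0.5%; Protocol Sections 1.2.2.2 and 1.2.2.3). Those rates do not show when subjects left or whether a MADRS was obtained.
- A reader might think that these subjects vanish from the report. SAP Section 7.1 tabulates treated, discontinued by reason, and analysis-set membership by group, and listing SUBEX-1.1 names exclusions.

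**Conclusion.** The point holds as a matter of population. The four MNAR tables cannot include a treated dropout without a usable post-baseline MADRS, and the error runs one way, towards apparent robustness. The size is conditional on a count that the documents do not give: none with 0 such subjects, roughly 5% to 6% with 1 brexpiprazole subject per group, 10% to 13% with 2, and about 25% or more only with 4 to 5. These figures rest on the design difference and SD, about 17 dropouts per group, and a worsening shift. The documents do not support a single headline percentage, nor any doubt about the primary MMRM under MAR. Low severity: a cheap improvement to the sensitivity analyses.

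**What to change.** In SAP Section 8.1.2.1, and in the titles of CT-5.11.1 to CT-5.11.4, define the population as all randomised subjects with at least one Phase B dose and a baseline MADRS, or add a repeat of the four tables on that population. Where no usable post-baseline score exists, impute Weeks 1 to 6 from baseline and group in the monotone regression already planned, using the placebo-based model for brexpiprazole subjects in the placebo-based analysis. Place these subjects in the tipping-point sets by their recorded reason for discontinuation. Keep the primary MMRM on the FAS.

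The cost is a sentence or two in the SAP and a slightly larger imputation dataset, with no new data collection. The downside is a slightly less favourable tipping point and placebo-based estimate.

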IREImmediately reportable eventIMIntermediate metabolizerIRBInstitutional review boardIWRSInteractive web response systemJSMDJapanese Society of Mood DisordersLDHLactate (lactic acid) dehydrogenase

LDL Low-density lipoprotein

LOCF Last observation carried forward LSMD Least square mean difference

MADRS Montgomery Åsberg Depression Rating Scale

MADRS-S The Montgomery Åsberg Depression Rating Scale Self-assessment

Abbreviation Definition

MAO inhibitor Monoamine oxidase inhibitor

MOR Missing at random

MedDRA Medical Dictionary for Regulatory Activities MHLW Ministry of Health, Labour and Welfare

MMRM Mixed-model repeated measures

MNOR Missing not at random

NGSP The National Glycohemoglobin Standardization Program

OC Observed Cases

PANSS Positive and Negative Syndrome Scale

PM Poor metabolizer

PQC Product quality complaint

PT Prothrombin time

PT (INR) Prothrombin time (international normalized ratio)

QTc QT corrected for heart rate

QTcB QT corrected for heart rate by Bazett's formula QTcF QT corrected for heart rate by Fridericia's formula

QTcN QT corrected for heart rate by FDA Neuropharmacological Division formula

SDS Sheehan Disability Scale

SIGH-D Structured Interview Guide for HAM-D
SIGMA Structured Interview Guide for MADRS
SNRI Serotonin-noradrenaline reuptake inhibitor
SSRI Selective serotonin reuptake inhibitor
T3/T4 Triiodothyronine/levothyroxine

TEAE Treatment-emergent adverse event; adverse event occurring after initiation of IMP

administration in the double-blind period (Phase B)

TSH Thyroid-stimulating hormone γ -GTP γ -glutamyl transpeptidase

1 Introduction

Depression is a condition that often takes a chronic course, causing significant suffering and imposing a burden on the patient. The disease interferes with the daily activities and social life of patients, who continue to suffer from decreased social functioning unless the disease remits. Moreover, depression is one of the major risk factors for suicide and, according to a psychological autopsy study, 60% to 70% of those who committed suicide had been diagnosed with depression. The number of suicides in Japan, even though a downward trend has been noted since 2012, was 21897 in 2016, which is still high compared with other developed countries. According to a published report by the Ministry of Health, Labour and Welfare (MHLW), the economic loss from depression resulting in leaves of absence from work, loss of employment, or suicide, etc, is estimated to be approximately 2.7 trillion yen in 2009. Decreased social functioning and increased suicide rate attributable to depression have become serious social problems. Under this circumstance, treatment of depression plays an important role in society.

The lifetime and 12-month prevalence of major depressive disorder in Japan were 6.2% and 2.1%, respectively, according to "Study on Mental Health Epidemiological Survey," a study supported by the Health and Labour Sciences Research Grants from fiscal year 2004 to 2006. The Treatment Guidelines issued by the Japanese Society of Mood Disorders (JSMD) (hereinafter referred to as JSMD Treatment Guidelines) list pharmacotherapy with antidepressants as the mainstay in the treatment of major depressive disorder. As first-line agents, the guidelines recommend the following novel antidepressants: selective serotonin reuptake inhibitors (SSRIs), serotonin-noradrenaline reuptake inhibitors (SNRIs), and mirtazapine, a noradrenergic and specific serotonergic antidepressant. However, remission rates in patients treated with these antidepressants are as low as 30% to 40%. This difficulty in improving or achieving remission of major depressive disorder symptoms interferes with social functioning, causing various issues including loss of employment, withdrawal from education, and divorce.

In the JSMD Treatment Guidelines,⁶ the following therapeutic methods are recommended for patients who fail to respond to the initial treatment with first-line agents such as SSRIs, SNRIs, and mirtazapine: Increase the dose to a sufficient level within the range in which adverse reactions are not clinically problematic; treat at the sufficiently increased dose for approximately 4 weeks; and then either change the drug if the patient does not respond to the treatment, or perform augmentation therapy if improvement is noted only in some of the symptoms of depression. Agents used for augmentation therapy include lithium, triiodothyronine/levothyroxine combination

(T3/T4), lamotrigine, valproic acid, carbamazepine, and atypical antipsychotics. While augmentation therapy with lithium has been reported to potentiate the antidepressant effects of drugs in many placebo-controlled studies, most of the drugs investigated in such studies were tricyclic antidepressants. Therefore, little data are available on augmentation of SSRIs or SNRIs at present. As a result of a meta-analysis on lithium toxicity profile, renal impairment, hypothyroidism, increased blood calcium level, and hyperparathyroidism were reported as adverse effects of particular concern. Special attention should be paid to the occurrence of these adverse effects during treatment with lithium. Concerning augmentation therapy with T3/T4, most of the available data are also from studies on tricyclic antidepressants. Furthermore, the efficacy of augmentation therapy with lamotrigine, valproic acid, or carbamazepine has not been sufficiently investigated. In addition, augmentation therapy with lithium, T3/T4, lamotrigine, valproic acid, or carbamazepine has not been approved for the indication of depression.

Meanwhile, concerning augmentation therapy with atypical antipsychotics mediated by the dopaminergic system, aripiprazole is the only antipsychotic agent that has been approved in Japan for use as an adjunctive therapy for the treatment of major depressive disorder. The efficacy of aripiprazole was confirmed in a Japanese double-blind, placebocontrolled trial (031-08-001)¹⁰ and 3 overseas double-blind trials of aripiprazole. However, the results of these clinical trials suggest that a certain percentage of patients cannot tolerate long-term use of aripiprazole as adjunctive therapy due to adverse events (AEs) such as akathisia and insomnia. This drawback of aripiprazole as an adjunctive therapy remains a therapeutic issue.

Brexpiprazole is a new chemical entity discovered by Otsuka Pharmaceutical Co., Ltd. Unlike aripiprazole, brexpiprazole, even at a low level of < 1 nM, exhibits serotonin (5-HT)_{1A} receptor partial agonist activity, 5-HT_{2A} receptor antagonist activity, and dopamine D₂ receptor (D₂ receptor) partial agonist activity with optimal intrinsic activity. The pharmacology of brexpiprazole is believed to be mediated by a combination of high binding affinity and functional activities at multiple monoaminergic receptors. It modulates the serotonergic and dopaminergic systems with its partial agonist activity or antagonist activity. In addition, for adrenergic $\alpha_{1B/2C}$ receptors, it also has similar subnanomolar binding affinity and antagonist activity. These 5-HT_{1A}/D₂ receptor partial agonist activities and 5-HT_{2A} and $\alpha_{1B/2C}$ receptor antagonist activities of brexpiprazole are thought to contribute to the antipsychotic, antidepressant, and impulse-control effects. Having the optimal intrinsic activity for D₂ receptors and potent effects on the serotonergic system compared with aripiprazole, brexpiprazole is expected to contribute

to a reduction in the incidence and severity of adverse reactions, such as akathisia and insomnia, which are issues associated with treatment using aripiprazole.

In Japan, brexpiprazole was investigated in a double-blind, placebo-controlled trial in patients with an acute relapse of schizophrenia (331-10-002)¹⁴ and in a long-term trial in outpatients with schizophrenia (331-10-003).¹⁵ Based on the results of these trials as well as overseas clinical trials, an application was filed for marketing authorization of brexpiprazole for the indication of schizophrenia, which was approved in January 2018.¹⁶

Outside Japan, double-blind, placebo-controlled trials in patients with an acute relapse of schizophrenia (331-10-230 and 331-10-231) were performed, and the results confirmed the efficacy of brexpiprazole and demonstrated its safety. In addition, double-blind, placebo-controlled trials in patients with major depressive disorder who had insufficient responses to SSRIs or SNRIs (331-10-227 and 331-10-228) were performed, and the results confirmed the efficacy of brexpiprazole as adjunctive treatment and demonstrated its safety in this patient population. Based on the results of the above clinical trials, brexpiprazole was approved in the US not only for the indication of schizophrenia but also received approval as adjunctive treatment of major depressive disorder.

As shown above, outside Japan, the efficacy of brexpiprazole was demonstrated not only in treating schizophrenia but also as adjunctive treatment for major depressive disorder. Therefore, brexpiprazole as adjunctive therapy is also likely to be effective in Japanese patients with inadequate response to antidepressants. The results of overseas clinical trials show that there are no safety-related concerns associated with brexpiprazole as adjunctive therapy. Therefore, use of brexpiprazole as adjunctive therapy is expected to reduce the incidence of adverse reactions such as akathisia and insomnia, which are issues associated with augmentation therapy using aripiprazole, and to enhance treatment adherence.

Based on the above, considering that it would be useful for the treatment of patients with major depressive disorder to investigate the efficacy and safety of brexpiprazole as adjunctive therapy in Japanese patients with inadequate response to antidepressants, we have planned to conduct this clinical trial.

